**Table 12 Adjuvant Time and Event Table for Pathologic Non-Responders (spartalizumab, dabrafenib and trametinib)**

	Post Operat iv eh	Week 12 i	Week 16 i	Week 20 i	Week 24 i	Week 28 i	Week 32 i	Week 36 i	Week 40 i	Week 44 i	Week 48 i	Week 52 i	EOT j
Concurrent medications	X	X	X	X	X	X	X	X	X	X	X	X	X
AEs	X	X	X	X	X	X	X	X	X	X	X	X	X
PE/Vitals/ECO Ga		X	X	X	X	X	X	X	X	X	X	X	X
CBC with diff		X	X	X	X	X	X	X	X	X	X	X	X
Serum chemistry b		X	X	X	X	X	X	X	X	X	X	X	X
TSH, fT4				X			X			X			
Echocardiogram c		X			X			X			X		
12-lead EKG		X			X			X			X		X
Research Biopsy d													
If evidence of disease recurrence or metastasis													
Research Blood e		X			X			X			X		X
Research microbiome collection f		X						X					X

Disease Assessment g				X			X			X			X
Spartalizumab		X	X	X	X	X	X	X	X	X	X		
Dabrafenib and trametinib dosing	X	Continuous Daily Dosing											

- a. Includes systolic and diastolic blood pressure, pulse rate, temperature and weight.
- b. Albumin, alkaline phosphatase, total bilirubin, bicarbonate, BUN, calcium, chloride, creatinine, glucose, LDH, magnesium, phosphorus, potassium, total protein, AST, ALT, sodium.
- c. Repeat echocardiogram will be performed at month 3 and 6 and at the discretion of the investigator if there are symptoms concerning for heart failure.
- d. Should a biopsy be performed as part of standard practice, this study may request up to 4 additional cores for correlative studies.
- e. 50ml of blood will be obtained at each time point for correlative correlates.
- f. Microbiome will be collected at week 12, 36 and at recurrence. OMNIgene kits, or equivalent, will be provided
- g. PET/CT or CT of the chest, abdomen, pelvis (neck if clinically indicated) and brain MRI (or CT of the head with contrast if MRI is contraindicated).
- h. Dabrafenib and trametinib combination therapy will resume approximately two days after the patient is able to resume normal oral intake and ideally should be within 2 weeks of date of surgery. This visit could be a telephone assessment by research nurse
- i. These time points are +/- 7 days.
- j. End of treatment is defined as completion of 44 weeks of adjuvant dabrafenib/trametinib, experiencing SAE or intolerable AE mandating discontinuation of treatment or the development of progressive disease

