## 4.7 BIOMARKER ANALYSES

Tumor samples may be assessed for expression of immune or melanoma related genes, RNAs, and/or proteins to identify molecular or immune features of response and resistance. Methodologies may include, tissue availability permitting, single stain

immunohistochemistry (IHC) or multiplex IHC, DNA profiling (WES or targeted panel, TCR sequencing), expression profiling (RNAseq or panel-based such as Nanostring).

Analyses on blood may include flow cytometry, ctDNA, CTC, proteomics, cytokine, and exosomal studies. Additional immune and molecular analyses may be conducted per the discretion of the study team.

In addition to immune studies, we may assess circulating tumor cells (CTC) and circulating free DNA (cfDNA) in these patients during the course of therapy. Our hypothesis is that the levels of CTC and cfDNA will correlate with disease burden, and will decrease during therapy and will rise at time of relapse. We will use a microfluidics system to isolate and enrich CTC from peripheral blood at baseline, at week 3 on neoadjuvant therapy, at Week 8 (surgery), and at Weeks 12, 24 and 36 post surgery). Blood will also be drawn at relapse (when applicable) and these assays will be performed. We will use cfDNA plasma to perform ddPCR to determine CNV for two mutations (V600K and V600E).

There is a growing appreciation of the influence of host factors on treatment to therapy in patients with cancer, such as microbiome. Microbiome samples collected from these patients will provide insight into this patient population, previously unstudied. Analyses of the gut microbiome samples may include 16s or metagenome sequencing.

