## 4.8 IMAGING ASSESSMENTS

Disease assessment will include imaging (computed tomography, magnetic resonance imaging) and physical examination (as indicated for palpable/superficial lesions). At screening, an MRI or CT of the head is required. At minimum, CT of the chest, abdomen and pelvis are required but additional imaging of affected areas (neck or extremities) may be required for documentation of target lesions.

Disease assessment will be completed within 35 days prior to the first dose of study drug, then as indicated in the Time and Events Tables Section 4.3. It is not necessary to repeat radiologic assessments at the final study visit if the subject was withdrawn due to disease progression. More frequent disease assessments may be performed at the discretion of the investigator. To ensure comparability between baseline and subsequent assessments, the same method of assessment and the same technique will be used when assessing response.

Disease response will be recorded as complete response (CR), partial response (PR), stable disease (SD), or progressive disease (PD) according to RECIST 1.1 criteria .

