### **Sample Size and Power**

A sample size argument will be based upon patients who do not have a pCR. We expect approximately 60% of enrolled patients to not achieve a pCR after 8 weeks on the dabrafenib/trametinib combination. Historically, these patients experience a 12-month relapse-free survival (RFS) rate of 50%, and we hope to increase this to 75%. Under the assumptions of 2 years for patient accrual and an additional 2 years of follow-up after accrual ends, exponentially- distributed RFS times, and a two-sided exponential maximum-likelihood test with a 5% Type 1 error rate (alpha), a total of 24 non-pCR patients will provide 80% power to detect a minimum increase in RFS at 1 year to 75%. If 60% of patients do not have a pCR, we would need to enroll a total of 40 patients to have a total of 24 non-pCR patients, but to account for a potentially higher pCR rate and patient dropout, we will accrue a total of 45 patients.

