### **Statistical Analyses**

For the primary objective, separately by group (patients who do/do not achieve a pCR at 8 weeks), the 12-month RFS rate will be estimated with a 95% confidence interval by using the Kaplan-Meier method. RFS is defined from time of surgery to any recurrence event (local or distant disease development or death due to melanoma. In addition, in patients who do not achieve a pCR, the 12-month RFS rate will be compared with the historical rate of 50% by using a two-sided exponential MLE test. Cox proportional hazards regression models will be fit to assess the association between various clinical, demographic, and disease covariates and RFS separately by pathologic response group.

For safety, the rate of grade 3+ adverse events will be tabulated and presented by group. For overall survival (OS) and distant metastasis-free survival (DMFS), 12-month rates will be reported with 95% confidence intervals, and Cox regression models will be used to assess the association between similar covariates as above and both OS and DMFS separately by group. OS is defined as time from treatment initiation to death. DMFS is defined as time from treatment initiation to development of documented distant metastatic disease outside the loco-regional site of the primary tumor or lymph node metastasis.

For the exploratory objectives, immunological and molecular features will be assessed quantitatively at baseline and at surgical resection. Kruskal-Wallis tests will be used to compare these parameters at each time point between responders (pCR) and non-responders (no pCR). Changes in each parameter from baseline to surgery will also be compared between responders and non-responders. Circulating tumor markers will be assessed at baseline and several on-study time points. Markers and changes in markers over time will be compared between responders and non-responders by using Kruskal-Wallis tests. In addition, generalized linear mixed models may be used to model these markers over time.

Finally, to assess the impact of neoadjuvant therapy on surgical resectability, a survey will be provided to surgeons regarding the difficulty of surgery (Appendix D). These data will be subjective and will be summarized graphically as numbers permit.

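### The last scheduled disease assessment falls about 44–48 weeks after surgery for an uninterrupted completer, short of the 12-month point at which the primary RFS rate is read

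*Combined protocol and SAP*

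**What the plan says.** - **Endpoint.** Section 7.0, Statistical Analyses: "RFS is defined from time of surgery to any recurrence event", and "the 12-month RFS rate will be estimated with a 95% confidence interval by using the Kaplan-Meier method".
- **Imaging schedule.** Section 4.8 has a baseline assessment, "then as indicated in the Time and Events Tables Section 4.3". Tables 11 and 12 mark adjuvant disease assessments at weeks 20, 32, 44 and EOT. The week-52 column has none, and no column follows EOT.
- **End of treatment.** Footnote j, the same in both tables: "End of treatment is defined as completion of 44 weeks of adjuvant dabrafenib/trametinib, experiencing SAE or intolerable AE mandating discontinuation of treatment", or progressive disease. Footnote h has dabrafenib and trametinib resume ideally within 2 weeks of surgery. The 7-day window in footnote i is attached to the week columns; none is given for EOT.
- **Extra imaging.** Section 4.8: "More frequent disease assessments may be performed at the discretion of the investigator". The same section mentions a final study visit ("It is not necessary to repeat radiologic assessments at the final study visit if the subject was withdrawn due to disease progression") but does not define or time it.
- **Follow-up.** Section 7.0, Sample Size and Power: "Under the assumptions of 2 years for patient accrual and an additional 2 years of follow-up after accrual ends". Section 2.2 includes recurrence patterns, DMFS and OS in all treated patients.
- **Week origin.** Section 3.0 adds 44 adjuvant weeks to 8 neoadjuvant weeks to make one year of therapy. Section 4.7 places blood sampling at baseline, on neoadjuvant therapy, at surgery, "and at Weeks 12, 24 and 36 post surgery".

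**The concern.** The RFS clock starts at surgery, while the scan schedule is tied to treatment, which began about 8 weeks earlier. EOT imaging therefore comes before 12 months of RFS for a patient who completes on time, and earlier still for one who stops dabrafenib and trametinib early. What happens between EOT and the landmark is learned only from discretionary scans or symptoms, so ascertainment can differ between patients just where the primary rate is read.

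The interval matters in this population. Section 1.3 reports 8 predominantly brain recurrences among 15 non-pCR patients in the predecessor study: 5 on adjuvant treatment and 3 shortly after the treatment year ended. It gives no exact times and the adjuvant regimen differed, so this shows relevance, not size. Brain imaging is part of the scheduled disease assessment (footnote g), so the missing visit is also a missing scheduled brain scan. Table 11 has the same gap, which affects the secondary 12-month RFS rate in pCR patients.

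**Working it through.** **1. Week origin.** The plan's own sum is 8 + 44 = 52 weeks, one year of therapy (Section 3.0). That reproduces only if week labels count from the start of neoadjuvant treatment, which puts week 52 about 44 weeks after surgery. Section 4.7 suggests counting from surgery for blood samples. On either reading, footnote j ties EOT to 44 adjuvant weeks and the week-52 column has no scan.

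**2. Timing of EOT.** 12 months = 365.25/7 = 52.2 weeks. Weeks from surgery to EOT = restart delay + 44:

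| Restart after surgery | EOT, weeks after surgery | Short of 12 months |
|---|---|---|
| 0 weeks | 44 | 8.2 weeks |
| 2 weeks (footnote h) | 46 | 6.2 weeks |
| 4 weeks (the week-12 visit) | 48 | 4.2 weeks |

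Holds are allowed (Section 3.3.2), and the text does not say whether held weeks count toward the 44. If they do not, a patient who restarts at 2 weeks needs 52.2 − 46 = 6.2 weeks of holds for EOT to reach 12 months.

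**3. Effect on the Kaplan-Meier estimate.** Use the plan's exponential assumption and its two rates, 50% and 75%. Let S be the true 12-month rate and w the EOT week.

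- RFS at EOT: S_E = S^(w/52.18).
- Chance of relapse between EOT and 12 months, given relapse-free at EOT: q = 1 − S/S_E.
- Let c be the share of those relapses that are found, and f the share of relapse-free patients with status recorded to 12 months. Everyone else is censored at EOT.
- Approximate 12-month estimate: S_E × [1 − cq/(cq + f(1 − q))]. With no ascertainment after EOT it is S_E carried forward.

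Example, S = 75%, w = 44: S_E = 0.75^0.843 = 0.785 and q = 0.044. With c = 1 and f = 0.5, the estimate is 0.785 × [1 − 0.044/(0.044 + 0.478)] = 0.718.

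| Ascertainment after EOT (assumption) | True 75%; EOT 44 / 46 / 48 | True 50%; EOT 44 / 46 / 48 |
|---|---|---|
| None | 78.5 / 77.6 / 76.7 | 55.7 / 54.3 / 52.9 |
| Half of relapses found, all relapse-free followed | 76.7 / 76.3 / 75.9 | 52.7 / 52.1 / 51.4 |
| All relapses found, half of relapse-free followed | 71.8 / 72.6 / 73.3 | 45.3 / 46.3 / 47.4 |
| Equal shares (c = f), or complete | 75 | 50 |

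The range is 1.7 to 5.7 points high and 1.7 to 4.7 points low. When c = f the formula returns S exactly, so bias needs unequal ascertainment or none at all. Simulation with n = 24 gave results within about half a point of these figures.

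**4. Scale.** The approximate 95% half-width at 75% with 24 patients is 1.96 × √(0.75 × 0.25/24) = 0.173, or 17 points.

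**5. The test against 50%.** The exponential estimate is events divided by time at risk. If each patient's time stops at the last assessment, a constant hazard gives the same rate whether that is week 44 or week 52, so the timing of EOT alone does not bias it. Section 7.0 states no censoring rule, so this is an assumption. In the one-sided case above (c = 1, f = 0.5, S = 75%, w = 44, data to 12 months), the rate is 0.25/(0.8690 − 0.5 × 0.75 × 0.157) = 0.309 per year. That implies 73.4% at 12 months, a shift of about 1.6 points against 3.2 for Kaplan-Meier.

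**The case against.** The strongest reply is that follow-up past EOT is plainly intended. The sample-size text assumes two further years after accrual ends, Section 2.2 needs recurrence and survival data, Section 4.8 allows extra scans, and the tables foresee a biopsy at recurrence. All of that stands. A reader might infer that data collection stops at EOT, so that the 12-month rate cannot be estimated or the trial loses power. The documents do not support either inference, and no power claim is made here. What remains is that no passage says when anyone is to be assessed after EOT.

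It is also fair that the uninterrupted completer may not be typical. Section 3.3.1 reports that all patients in the cited triplet study needed dose adjustment or interruption, and EOT could move later if held weeks do not count. But that rule is not stated, and early stoppers move the other way.

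Finally, adverse event recording to 150 days after the last dose might seem to supply relapse status at 12 months. It does not: Section 5.0 sets a recording period without a visit, and Section 5.1 excludes expected progression of the disease under study.

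**Conclusion.** The point holds as a scheduling gap that should be fixed. For a patient who restarts within 2 weeks and has no long holds, the last scheduled assessment comes 6–8 weeks before the primary landmark, or about 4 weeks if the 44 weeks run from the week-12 visit. The Kaplan-Meier estimate could then be off by about 2–6 points upward if relapses after EOT are not ascertained, or 2–5 points downward if they surface while half of the relapse-free patients have no recorded status. It is close to unbiased when ascertainment is complete or equally incomplete. These figures assume a constant hazard and the stated ascertainment shares; the documents do not say which pattern would occur.

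A reader might also infer that the primary comparison with 50% is compromised. That does not follow: under its own constant-hazard assumption the exponential test is not materially biased, and the shifts in the estimate are small beside its 17-point half-width.

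**What to change.** 1. **Anchor an assessment to the endpoint.** In Tables 11 and 12 and Section 4.8, schedule a disease assessment at 12 months from surgery (± 7 days) for every relapse-free patient, whatever the reason treatment stopped. Say that a relapse found at that assessment counts toward the 12-month rate, and record relapse status for relapse-free patients through the end of the window.
2. **Add a status line after EOT.** Put relapse and survival status in the schedule, consistent with the two years of follow-up after accrual in Section 7.0 and no shorter.
3. **Settle the calendar.** Reconcile the week origin in Section 4.7 with Section 3.0 and the tables, and state whether held weeks count toward the 44.

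Cost: an amendment to two tables and a few sentences. Re-timing the EOT disease assessment needs no extra scan for completers. Its downside is a gap of about 16 weeks after the week-44 scan (8 + 52.2 − 44 = 16.2, against 12 between the earlier adjuvant scans) and no scan at end of treatment. Keeping the EOT scan as well avoids that at one extra scan per completer. Early stoppers need contact and a scan at 12 months that the tables do not now provide.

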## 4.4 SAFETY EVALUATIONS

### 4.4.1 Physical exams/ECOG/Vital Signs

A complete physical examination will be performed by a qualified physician or a midlevel provider (physician's assistant, nurse practitioner). Documentation of Eastern Cooperative Oncology Group status is required.

Baseline skin exam must be performed. Skin photography of new skin lesions or lesions that change during therapy recommended at each reassessment while the subject is on therapy.

Vital sign measurements will include systolic and diastolic blood pressure, pulse rate, and temperature. On days where vital signs are measured multiple times, temperature does not need to be repeated.

The performance status assessment is based on the ECOG scale:

- 0 Fully active, able to carry on all pre-disease performance without restriction.
- 1 Restricted in physically strenuous activity but ambulatory and able to carry out work of a light or sedentary nature (e.g., light house work or office work).
- 2 Ambulatory and capable of all self-care but unable to carry out any work activities. Up and about more than 50% of waking hours.
- 3 Capable of only limited self-care, confined to bed or chair more than 50% of waking hours.
- 4 Completely disabled. Cannot carry on any self-care. Totally confined to bed or chair.

### 4.4.2 ECG

12-lead ECG will be obtained as indicated in the Times and Events Tables in Section 7.2. Each 12-lead ECG will be performed after the subject has rested at least five minutes in a semi- recumbent or supine position.

$$QTc \text{ (Bazett)} = \frac{QT}{\sqrt{RR}}$$

Those QTc values greater than 480msec as calculated by the machine must be confirmed manually using Bazett's formula given below:

If there are any clinically significant abnormalities including but not limited to a QTcB > 500msec, confirm with two additional ECGs taken at least 5 minutes apart.

#### **4.4.3 Echocardiogram**

An echocardiogram will be performed to assess cardiac ejection fraction and cardiac valve abnormalities as indicated in the Times and Events Tables in Section 7.2.

Echocardiography should include an evaluation for left ventricular ejection fraction and both right- and left sided valvular lesions. For each subject, the same procedure should be performed at the screening and as clinically warranted during the course of the study.

#### **4.4.4 Ophthalmic**

Patients will have a standard ophthalmic exam performed by an ophthalmologist at screening. The exam will include indirect fundoscopic examination, visual acuity, visual field examination, tonometry, and direct fundoscopy, with special attention to retinal abnormalities that are predisposing factors for RVO or CSR.

### **4.5 LABORATORY ASSESSMENTS**

Hematology, clinical chemistry, and additional parameters to be tested are listed below:

**Hematology**

Platelet Count	RBC Indices:	Automated WBC Differential:
WBC Count (absolute)	MCV	Neutrophils
Hemoglobin		Lymphocytes
Hematocrit		Monocytes
		Eosinophils
		Basophils

**Clinical Chemistry**

BUN	Potassium	AST (SGOT)	Total and direct bilirubin
Creatinine	Chloride	ALT (SGPT)	Total protein
Glucose	Total CO 2	Lactate dehydrogenase (LDH)	Albumin
Sodium	Calcium	Alkaline phosphatase	Phosphorus
Magnesium	TSH	Free T4	

## 4.6 BIOMARKER COLLECTIONS AND ANALYSES

### Biospecimen Collection

For blood and tissue correlative studies, specimens will be collected as part of the protocol study assessments and stored for later analysis. Missed tissue or blood collections, will not be classed as a deviation. Below are proposed analysis for tissue and blood as availability and quality of each permits. The priority of analysis will be determined by investigators.

In the neoadjuvant setting, patients will have mandatory baseline biopsy as well as research collection of part of the surgical sample. On the occasion where available tissue or blood is limited and we did not receive enough for analysis or where the tissue or blood collection was missed, specimens collected from MD Anderson patients at the same time points as part of protocol 2012- 0846 and/or LAB00-063 may be requested for use as long as the patient has a valid informed consent.

Available paraffin embedded tumor tissue from prior biopsies or excisions may also be collected as pre-treatment comparator samples, so long as the patient provides consent for use in this study.

Tissue will be collected as per the Institute guidelines and standard operating procedures. All samples will be processed, labeled, and stored in accordance with NCI best practices for biospecimens. General details regarding tissue procurement are indicated below:

Tumor Tissue: Each set of core biopsies or surgical specimen may be divided in up to 4 portions and processed as below for later analysis:

- (1) FFPE for histology and IHC (25% of the specimen, or 1 core biopsy)
- (2) Snap frozen tumor in a cryovial (75% of the specimen or 3 core biopsies)

### Blood processing and storage for circulating correlative analysis:

Two 10 ml tubes of blood will be collected for PBMC isolation and cryopreserved, for subsequent evaluation. Plasma will be collected and stored at -80°C. One 10ml serum will be collected and stored at -80°C. Two 10ml tubes of blood will be collected for cfDNA and genomic DNA, for analysis of circulating tumor markers and genomic analysis.

Stool samples for microbiome analysis: OMNIgene Gut Kits, or equivalent, will be provided for stool sampling for microbiome analysis. The kits come with full instructions on use (Appendix C).

## 4.7 BIOMARKER ANALYSES

Tumor samples may be assessed for expression of immune or melanoma related genes, RNAs, and/or proteins to identify molecular or immune features of response and resistance. Methodologies may include, tissue availability permitting, single stain

immunohistochemistry (IHC) or multiplex IHC, DNA profiling (WES or targeted panel, TCR sequencing), expression profiling (RNAseq or panel-based such as Nanostring).

Analyses on blood may include flow cytometry, ctDNA, CTC, proteomics, cytokine, and exosomal studies. Additional immune and molecular analyses may be conducted per the discretion of the study team.

In addition to immune studies, we may assess circulating tumor cells (CTC) and circulating free DNA (cfDNA) in these patients during the course of therapy. Our hypothesis is that the levels of CTC and cfDNA will correlate with disease burden, and will decrease during therapy and will rise at time of relapse. We will use a microfluidics system to isolate and enrich CTC from peripheral blood at baseline, at week 3 on neoadjuvant therapy, at Week 8 (surgery), and at Weeks 12, 24 and 36 post surgery). Blood will also be drawn at relapse (when applicable) and these assays will be performed. We will use cfDNA plasma to perform ddPCR to determine CNV for two mutations (V600K and V600E).

There is a growing appreciation of the influence of host factors on treatment to therapy in patients with cancer, such as microbiome. Microbiome samples collected from these patients will provide insight into this patient population, previously unstudied. Analyses of the gut microbiome samples may include 16s or metagenome sequencing.

